4.3.3 Pre-HCT Evaluations

The following observations must be performed within 30 days (unless noted otherwise) prior to enrollment. Subjects must also continue to meet eligibility criteria at the start of conditioning:

1. History, physical examination, height, and weight. The recommended history is to include the age at diagnosis, race/ethnicity, gender, and indications for HCT. In addition, for patients enrolled on the Treosulfan PK studies, the patient's height and weight must be repeated if not previously obtained within 30 days of the start of Treosulfan.
2. Karnofsky or Lansky performance status.
3. Disease Assessments including Genetic Testing:
 - a. Patients should have genetic testing to document their underlying BMFD (at any time prior to screening assessment for disease eligibility; this excludes patients with PNH).
 - b. Patients who lack a genetic mutation (excluding patients with PNH) must have negative testing for Fanconi anemia via Diepoxybutane (DEB) or Mitomycin C (MMC) testing on peripheral blood or skin fibroblasts (at any time prior to screening assessment for disease eligibility).
 - c. Patients who lack a genetic mutation (excluding patients with PNH) must have telomere testing by flow-FISH (at any time prior to screening assessment for disease eligibility).
 - d. For patients with PNH: flow cytometry for PNH per institutional practice. Repeat PNH testing within 30 days prior to enrollment.
4. HLA typing (patient and donor) and anti-donor antibody testing (if not already performed). HLA typing may be done more than 30 days prior to enrollment; however anti-donor antibody testing should be performed within 30 days of study enrollment.
5. Additional Laboratory Evaluations:
 - a. CBC with differential and platelet count
 - i. For patients enrolled on the Treosulfan PK studies, a CBC is required in the morning on days -6 and -5 prior to the start of the Treosulfan infusion. This can be done in conjunction with standard of care tests.
 - ii. For patients enrolled in the Biological Studies, a CBC is required to be done on the same day as the sample collection. This can be done in conjunction with standard of care tests.
 - b. Patient/Donor ABO/Rh
 - c. BUN and Creatinine
 - i. For patients enrolled on the Treosulfan PK studies, a serum creatinine is required in the morning on days -6 and -5 prior to the start of the Treosulfan infusion. This can be done in conjunction with standard of care tests.
 - d. Electrolytes: sodium, potassium, chloride, bicarbonate, calcium, magnesium, phosphorus
 - e. Liver function studies: total bilirubin, direct bilirubin, ALT, AST, and alkalinephosphatase
 - f. PT, PTT, INR

- g. Serum ferritin and % iron saturation
 - h. Quantitative immunoglobulins (IgG, IgA, and IgM) per institutional practice
 - i. Serum pregnancy test for females of childbearing potential
 - j. Baseline peripheral blood samples for chimerism analysis by molecular methods (patient and donor) at any time prior to study enrollment
6. Infectious Disease Evaluations per institutional practice. Recommend including:
 - a. CMV, HSV, VZV, and toxoplasma per institutional practice
 - b. Hepatitis B and C, HIV 1&2, HTLV 1&2, and syphilis per institutional practice
7. Radiological Evaluations:
 - a. CXR or chest CT as clinically indicated or per institutional practice. It is recommended that patients with a history of neutropenia or underlying immunodeficiency have a CT scan of the chest, abdomen and pelvis as well as the sinuses (if age appropriate) as part of their pre-transplant work-up due to increased risk for infection including fungal disease.
 - b. Cardiac
 - i. EKG
 - ii. Echocardiogram or MUGA for assessment of left ventricular ejection fraction (LVEF) or, for patients unable to obtain a LV EF, LV shortening fraction.
 - c. Pulmonary: pulmonary function testing to include FEV1, FVC, FEV1/FVC, TLC, RV, and DLCO (corrected for Hemoglobin). For patients who unable to perform PFTs due to age or developmental ability, pulse oximetry is an acceptable alternative.
 - d. Formal assessment of hepatic and/or cardiac iron overload within 6 months of study enrollment using a validated methodology such as T2* MRI (hepatic or cardiac), ferriscan (hepatic), or biopsy (hepatic) per institutional practice.
 - i. For patients ≥ 18 years with a history of significant transfusions defined as ≥ 8 packed red blood cell transfusions per year for ≥ 1 year or have received ≥ 20 packed red blood cell transfusions (lifetime cumulative) will require formal hepatic and cardiac iron measurement. In addition, patients with a prior history of hepatic or cardiac iron overload will also require formal assessment for hepatic and cardiac iron overload.
 - ii. For patients < 18 years old with a history of significant transfusions defined as ≥ 8 packed red blood cell transfusions per year for ≥ 1 year or have received ≥ 20 packed red blood cell transfusions (lifetime cumulative) will require formal hepatic iron measurement. In addition, patients with a prior history of hepatic iron overload will also require formal assessment for hepatic iron overload.
8. Bone marrow Evaluation: A bone marrow aspirate/biopsy for pathology, flow cytometry, cytogenetics and MDS FISH panel within 60 days prior to study enrollment. The MDS FISH panel should evaluate for deletion 5q/monosomy 5, monosomy 7/deletion 7q, trisomy 8, and deletion 20q.
9. Research Studies (Optional):

1. Treosulfan Pharmacokinetic Studies (Optional): Treosulfan pharmacokinetic sampling and analysis on peripheral blood samples will be done on days -6 and -5. The same sample will be used for both Treosulfan and Treosulfan monoepoxide quantitation (samples will be split in PK Lab during analysis process). PK samples must be drawn from a different lumen/venous access than the drug infusion. If this is not possible and blood sampling needs to occur from the same lumen for Treosulfan infusion, document on the Treosulfan PK worksheet.

The Treosulfan PK studies will be performed in approximately 5 patients for each of the following age groups: 1) 1 year to < 2 years, 2) 2 years to <4 years, 3) 4 years to <12 years and 4) ≥ 12 years (total patients: approximately 20). CBC with differentials and a serum creatinine is required in the morning on day -6 and -5 prior to the start of the Treosulfan infusion. This can be done in conjunction with standard of care tests (**Table 14 and Appendix E**).

Table 14: PK Sample Collection Schedule for Day -6 and Day -5 Treosulfan Infusions		
Time Point	Collection Window	Blood Volume
Pre-infusion	Within 5 minutes before starting Treosulfan infusion	1 mL
End-of-infusion (EOI)	EOI + 5 minutes	1 mL
EOI + 20 minutes	+/- 5 minutes	1 mL
3.5 hours after start of infusion	+/- 10 minutes	1 mL
6 hours after start of infusion	+/- 10 minutes	1 mL
9 hours after start of infusion	+/- 10 minutes	1 mL

2. Biological Studies (Optional): Baseline assessment

Blood and marrow samples will be obtained within 60 days prior to enrollment for somatic genomic analyses, T-cell phenotypes, and cytokine measurement. Those providing consent will have blood (3mL-5mL EDTA tube and 5mL in sodium heparin tube) and marrow samples (3mL-5mL in EDTA tube and 5mL in sodium heparin tube) sent to the central laboratory for these studies. A CBC with differentials is required to be done on the same day as the sample collection. This can be done in conjunction with standard of care tests. (**Appendix E**) If samples have been donated and subject does not continue to transplant, samples will be stored for future research.

3. Mutational Testing (Optional) – Baseline assessment

Individuals who have participated in previous genetic studies and who have no identified mutation will be eligible to participate in this whole exome/genome sequencing study (excluding patients with PNH). Those interested in participation will be asked to provide peripheral blood (10 or 20 ml, based on subject’s weight) in EDTA (purple top) tubes for DNA extraction after informed consent for whole exome/genome sequencing is obtained. (**Appendix E**)

4. Health Related Quality of Life (Optional): Baseline assessment

At the time a patient is identified as participating in the study, the CIBMTR Survey Research Group (SRG) is notified and then adds that patient to CIBMTR's electronic Patient Reported Outcomes (ePRO) system for long-term QOL tracking.

Pre-transplant (baseline) QOL data will be collected by the center or CIBMTR electronically or on paper forms within 30 days prior to HCT. If conditioning is delayed, the QOL surveys should be repeated so the QOL surveys are completed within 30 days prior to HCT. Electronically collected baseline QOL surveys will be directly entered in the ePRO system by the patient or proxy. The center will securely email, or fax baseline QOL instruments completed on paper to the SRG for entry into the ePRO system. (**Appendix H**)

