2.5.1.1.1 Treosulfan

Treosulfan will be administered intravenously over 120 minutes for three consecutive days (day -6 to -4). Actual body weight is to be used to calculate BSA for Treosulfan (**Appendix D**). However, for patients >120% of ideal weight, use adjusted weight to calculate BSA. See **Table 2** for dosing guidelines. Pharmacokinetic evaluation will be performed on days -6 and -5 (see **Appendix E**). On days -6 to -4, Treosulfan should be administered prior to fludarabine.

BSA	Dose
< 0.4	10 grams/m ² /day
≥ 0.4 – < 0.9	12 grams/m ² /day
≥ 0.9	14 grams/m ² /day

Note: The BSA should NOT be rounded to the “tenths” position. For example, if the patient’s BSA is 0.88 the BSA should not be rounded up to 0.9, it should remain 0.88. Therefore, if a patient had a BSA of 0.88, the Treosulfan dose based on BSA would be 12grams/m²/day. However, if a patient’s BSA is 0.848 this may be rounded to 0.85 per institutional practice.

Drug-Drug Interactions (DDI): DDI analysis predicted a weak (AUC ratio ≥ 1.25 and < 2) to moderate (AUC ratio ≥ 2 and < 5) interaction for CYP3A4, a weak interaction for CYP2C19, and a negligible (AUC ratio < 1.25) interaction for P-gp. Given the short duration of treatment with Treosulfan and its short t_{1/2} (2 hours), no dose adjustment of Treosulfan is recommended when inhibitors of CYP3A4, CYP2C19, or P-gp are co-administered. While the reduced dose of Treosulfan (10 g/m²/d × 3) also reduces the potential for DDI, the PBPK-based analysis still predicts a weak inhibitor potential for Treosulfan with CYP3A4 and CYP2C19. Considering overall timing of treatments and the respective PK properties of the concomitantly used drugs (e.g., t_{1/2}), the interaction potential can be reduced to “no interaction” (AUC ratio < 1.25), if all concomitantly used CYP3A4 and CYP2C19 substrate drugs are dosed 2 hours before or 8 hours after the 2-hour I.V. infusion of Treosulfan.

Note: The protocol recommends using methylprednisolone as a pre-medication prior to rabbit ATG and potentially again 4 and 8 hours after rabbit ATG. Although Methylprednisolone is a

major CYP3A4 substrate, this medication may be administered after Treosulfan even within the 8-hour time referenced above.

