5.5 Analysis Populations and General Analysis Guidelines

5.5.1 Primary Analysis Population

All patients conditioned with a Treosulfan-containing regimen will be included in the primary analysis population. Time to event analyses will start at initiation of conditioning (day -6 of transplant). Analyses for the primary endpoint, all secondary endpoints, and safety endpoints, will use the primary analysis population. The primary analysis will occur once all patients have been followed for 12 months, Endpoint Review Committee adjudication completed, and data is locked.

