5.8.2 Health-Related Quality of Life

PROMIS Scale total score and subdomain scores will be summarized using means and SDs at baseline, 6 months, and 1 year. Changes from baseline to day +180 and day +365 post-HCT will be analyzed using the paired t-test and linear mixed models for longitudinal data.

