APPENDIX H
QUALITY OF LIFE QUESTIONNAIRE USING THE PATIENT REPORTED
OUTCOMES MEASUREMENT INFORMATION SYSTEM (PROMIS)

QOL Study Design

The following instruments will be used to assess QOL within one month before transplant (Baseline), at 180 days and 1-year post-transplant. Only English- or Spanish-speaking trial participants aged 5 years and older will be included in the QOL collection. Patients aged 8-17 at the time of assessment will complete pediatric instruments. Proxy reports (e.g., parents,guardians) will be collected for patients aged 5 to 8.

At the Baseline time point, center or CIBMTR staff will administer QOL instruments electronically or on paper. At 180 day and 1 year time points, the CIBMTR will administer the QOL surveys electronically or on paper, per respondent need or preference. Each time point will take about 2-3 minutes to complete.

PROMIS Global

The PROMIS Global measure contains 10 items for adults and 9 items for pediatric patients (self- or proxy-report), with two summary scores for physical and mental functioning. The median score is 50 with a standard deviation of 10. Higher scores indicate better QOL⁶⁸.

Subject/Patient Reported Outcomes (PRO)

This includes all items/questions included on each patient- or proxy-reported QoL survey.

PROMIS Scale – Global Health (adult self-report)

Please respond to each question or statement by marking one box per row

	Excellent	Very good	Good	Fair	Poor
In general, would you say your health is:					
In general, would you say your quality of life is:.					
In general, how would you rate your physical health?					
In general, how would you rate your mental health, including your mood and your ability to think?					
In general, how would you rate your satisfaction with your social activities and relationships?					

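### The quality-of-life baseline window runs to the day of transplant, so a survey taken during conditioning counts as baseline; age 8 also falls in both the proxy and the self-report group

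*Protocol*

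**What the plan says.** Section 4.3.3 ties the pre-transplant work-up to enrollment: "The following observations must be performed within 30 days (unless noted otherwise) prior to enrollment". The quality-of-life survey (item 9.4) is one of the exceptions: "Pre-transplant (baseline) QOL data will be collected by the center or CIBMTR electronically or on paper forms within 30 days prior to HCT". The next sentence adds: "If conditioning is delayed, the QOL surveys should be repeated so the QOL surveys are completed within 30 days prior to HCT". Appendix H gives the same anchor: "The following instruments will be used to assess QOL within one month before transplant (Baseline), at 180 days and 1-year post-transplant".

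Treatment begins before that anchor. Section 2.5.1.1.1 states: "Treosulfan will be administered intravenously over 120 minutes for three consecutive days (day -6 to -4"). Section 5.5.1 takes the same day as time zero for the survival-type analyses: "Time to event analyses will start at initiation of conditioning (day -6 of transplant").

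On the choice of form, section 3.3.4 and Appendix H say: "Patients aged 8-17 at the time of assessment will complete pediatric instruments". The synopsis, section 3.3.4 and Appendix H assign proxy report to ages 5 to 8.

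Section 5.8.2 gives the analysis: "Changes from baseline to day +180 and day +365 post-HCT will be analyzed using the paired t-test", together with linear mixed models.

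**The concern.** A baseline for a conditioning regimen should describe the patient before the regimen starts. Here the limit is the transplant, and the whole regimen is given between day -6 and that limit. A survey completed on day -1 meets the written rule, yet its 7-day recall items on fatigue and pain look back over every day of conditioning. Tables 7a, 7b and 9 list nausea and vomiting among the most frequent effects of Treosulfan and Thymoglobulin, so the expected effect on a score taken then is downward. Each later score is compared with that baseline, so a lowered baseline would show up as improvement.

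This cannot be repaired at analysis. A statistical analysis plan can flag late surveys, but it cannot supply a pre-conditioning score that was never collected.

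The second defect is smaller. An 8-year-old satisfies both the proxy rule and the self-report rule, so the respondent is left to the site and may differ between visits.

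**Working it through.** The protocol gives no sample size, effect or power for quality of life, so there is no figure to reproduce.

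**1. Anchors side by side**

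| Item | Place | Must be done before |
|---|---|---|
| General pre-transplant evaluations | 4.3.3, opening | enrollment |
| Biological study samples | 3.3.2 | start of the preparative regimen |
| Mutational testing | 3.3.3; Appendix E, Table 20 | start of the preparative regimen / conditioning |
| Quality-of-life baseline | 4.3.3 item 9.4; Appendix H | transplant (day 0) |

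Section 4.2 requires Segment A enrollment before study treatment, so the first three rows all precede conditioning. Only the quality-of-life window extends through it.

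**2. Overlap of the window with conditioning**

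Days -6 to -1 are 6 of the 30 permitted days: 6/30 = 20%. If day -6 is left out, because a survey that morning could precede the first infusion, the overlap is 5/30 = 17%. Each rest day added between conditioning and infusion (Table 1, footnote 4) adds 1/30, or 3.3 percentage points.

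**3. Possible bias in mean change**

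Bias = f × d, where f is the share of baselines taken during conditioning and d is the drop in score they carry. The protocol gives neither, so both are assumed.

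| f | d = 2 | d = 5 | d = 10 |
|---|---|---|---|
| 0 | 0 | 0 | 0 |
| 5% | 0.1 | 0.25 | 0.5 |
| 20% (even spread over the window) | 0.4 | 1.0 | 2.0 |

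Appendix H gives the score an SD of 10.

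**4. What such a bias does to the paired t-test**

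Assume no true change, an SD of change of 10 and 20 to 40 pairs (40 is the trial's full target). The noncentrality is (bias/10) × √n. For 1 point it is 0.1 × √20 = 0.45 up to 0.1 × √40 = 0.63. Two-sided rejection at a nominal 0.05:

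| Bias | n = 20 | n = 30 | n = 40 |
|---|---|---|---|
| 0 | 0.050 | 0.050 | 0.050 |
| 1 point | 0.071 | 0.083 | 0.095 |
| 2 points | 0.136 | 0.185 | 0.235 |

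**5. Patients whose form changes between visits**

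Take boundaries at the 8th and 18th birthdays, ages spread evenly (assumed), and 395 days from baseline to the 1-year survey (30 + 365). The share is 2 × (395/365.25) / (age range):

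- ages 5 to 50: 2.163/45 = 4.8%, or 1.9 of 40;
- ages 5 to 30: 2.163/25 = 8.7%, or 3.5 of 40;
- ages 5 to 22: 2.163/17 = 12.7%, or 5.1 of 40.

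These are upper counts, because children under 5, non-consenters and patients who die do not contribute. The effect on the score has no known direction.

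**6. After the fix**

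With the limit at the first conditioning dose, the overlap in step 2 is 0 and so is the bias in step 3.

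**The case against.** The best defence is that the protocol plainly intends an earlier survey. Table 13 lists PROMIS in its baseline column, separate from the column for days -6 and -5. The survey group is notified when a patient is identified as participating. Section 4.2 places enrollment at most 14 days before planned conditioning, about day -20, and a survey done then leaves some 10 days before it would fall outside the 30-day window. This stands. It makes on-conditioning baselines less likely but does not rule them out, because nothing in the text requires completion before the first dose.

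A reader might infer that the repeat rule makes matters worse: added rest days push a clean early survey outside 30 days and force a replacement taken during conditioning. The text does not say this. The rule is triggered by a delay of conditioning, when conditioning has not begun, and the rest-day footnote orders no new survey. What remains is that the rule measures compliance against the transplant, so a site could read it that way.

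A reader might also infer that every patient aged 7 or 17 at baseline switches form by one year. That does not follow. The final visit is 365 ± 28 days, so someone who has just turned 17 can still be 17 at that visit, and a child who turns 8 can stay on proxy report because of the overlap. Choosing the form by age at assessment is defensible, and handling of scores by form may properly sit in a statistical analysis plan.

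**Conclusion.** The point holds as a gap in a data-collection rule. The baseline window permits surveys on days -6 to -1, 20% of its length, and these could inflate apparent improvement. It would go too far to say that change from baseline is biased toward improvement. The bias is permitted, not shown; it is zero if all sites survey before day -6, and its size rests on a share and a score drop that the protocol does not give. With an even spread over the window and a drop of 2 to 10 points it is 0.4 to 2.0 points. At 1 to 2 points, with an SD of change of 10 and 20 to 40 pairs, the false-positive rate would rise from 5% to between about 7% and 24%. Form switching does not support a directional claim.

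The age-8 overlap is a plain inconsistency, whatever is assumed.

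The stakes are low. The endpoint is optional and exploratory in a single-arm trial, and the primary, secondary and safety results are untouched. The correction is still worth making because it is cheap and a missed pre-conditioning score cannot be recovered.

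**What to change.** 1. In section 4.3.3 item 9.4 and Appendix H, require the baseline survey after consent and before the first dose of conditioning, for example within 30 days before the start of conditioning.
2. State the repeat rule against the start of conditioning, so that a delay of the infusion alone does not call for a repeat.
3. Resolve age 8 in the synopsis, section 3.3.4 and Appendix H, for example proxy report from 5 to under 8 and self-report from 8.
4. Flag the few patients whose form or respondent changes between visits, or leave them out in a sensitivity analysis. Freezing the form at baseline age is not needed; it would keep some patients on a form outside the protocol's own age ranges.

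The cost is wording only. The one downside is that a survey not completed before conditioning becomes missing instead of late, so sites should collect it promptly once the patient is identified as participating.

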4.3.4 Post-HCT Evaluations – The Following Studies are Recommended

1. History and physical exam to assess GVHD and other morbidities weekly until Day +100, then at Day +180 and Day +365. GVHD evaluation and grading to be in keeping with the BMT CTN Technical guidelines. For scheduling purposes, a target day range has been provided in **Table 12**.
2. Karnofsky or Lansky performance status at Day +365.
3. Laboratory Evaluations – the following laboratory evaluations are required with the minimum frequency of monitoring; however, more frequent monitoring per institutional practice is allowed:
 - a. CBC with differential
 - i. Day 0 until count recovery/engraftment (defined as an ANC > 0.5 x 10⁹/Lx 3 consecutive measurements): Minimum three times per week.
 - ii. Count Recovery/Engraftment through day +100: Minimum weekly
 - iii. Day +101 through day +365: Minimum monthly
 - iv. For patients enrolled on the Treosulfan PK studies, a CBC is required in the morning on days -6 and -5 prior to the start of the Treosulfan infusion.
 - b. Blood Chemistries: sodium, potassium, chloride, bicarbonate, BUN, creatinine, calcium, magnesium, phosphorus:
 - i. Day 0 through Day +28: Minimum twice a week.
 - ii. Day +29 through day +100: Minimum weekly
 - iii. Day +101 through day +365: Minimum monthly
 - iv. For patients enrolled on the Treosulfan PK studies, a serum creatinine is required in the morning on days -6 and -5 prior to the start of the Treosulfan infusion.
 - c. Liver function studies: Total and direct bilirubin, alkaline phosphatase, AST, and ALT:
 - i. Day 0 through Day +28: Minimum twice a week
 - ii. Day +29 through day +100: Minimum weekly
 - iii. Day +101 through day +365: Minimum monthly

- d. Tacrolimus levels:
 - i. Day +1 through day +28: Minimum twice weekly
 - ii. Day +29 through day+100: Minimum weekly
 - iii. Day +101 through day+180 or initiation of tacrolimus taper whichever is later: minimum every other week then monthly per institutional practice.
 - iv. If there are concerns for renal dysfunction, the tacrolimus level should be followed more closely per institutional practice
 - e. Chimerism studies on peripheral blood: Myeloid and CD3
 - i. Day +28 (Day +28 chimerism should only be evaluated if the patient has anANC $\geq 0.5 \times 10^9/L$)
 - ii. Day +42 (Day +42 chimerism should only be evaluated if chimerism studies were not performed at day +28)
 - iii. Day +100, Day +180, Day +365
 - iv. For patients with mixed chimerism, follow up chimerism studies per institutional practice is recommended to document sustained engraftment or graft failure.
 - f. Peripheral blood CMV and EBV PCR monitoring:
 - i. CMV PCR: Day 0 through day +100 (minimum weekly) and then it is recommended to continue weekly or every other week monitoring of CMV by PCR in the peripheral blood through day 180 due to receipt of serotherapy. Additional monitoring should be per institutional practice for patients with a history of CMV reactivation/disease within the first 100 days or for those who remain on immune suppression.
 - ii. EBV PCR: Day 0 through day +100 (minimum weekly) and then it is recommended to continue weekly or every other week monitoring of EBV by PCR in the peripheral blood through day 180 due to receipt of serotherapy. Additional monitoring should be per institutional practice for patients with a history of EBV reactivation post-transplant.
 - g. Serum ferritin and % iron saturation: Day +365
 - h. Absolute lymphocyte numbers by flow cytometry for lymphocyte subpopulation to include CD3, CD4, CD19, and CD56 at day +100, +180 and +365.
 - i. Serum quantification of IgG, IgM, and IgA: Minimum at day +90, 180, and +365.
4. Bone marrow evaluation including pathology, flow cytometry, cytogenetics, and MDS FISH panel per the discretion of the treating physician at day +365. The MDS FISH panel should evaluate for deletion 5q/monosomy 5, monosomy 7/deletion 7q, trisomy 8, and deletion 20q.
5. Radiological Evaluations:
- a. Pulmonary function testing: FEV1, FVC, FEV1/FVC, TLC, RV, and DLCO (corrected for Hemoglobin) around day +365 in those patients who can perform PFTs.
 - b. T2* MRI of the liver and heart is recommended around day +365 in those patients with a history of iron overload pre-HCT or those considered at risk for iron overload post-HCT per institutional practice.

6. Toxicity assessments at Day +28, +56, +100, +180, and +365.
7. GVHD assessments: Patients should be assessed weekly until Day +100 post-transplant for GVHD. After Day +100, patients will be assessed at each follow-up visit through 12 months for the presence of GVHD.
8. Research Studies:
 - a. Biological Studies (optional): At day +365 post-HCT.
Blood and marrow samples will be obtained at one-year post-HCT for somatic genomic analyses, T-cell phenotypes, and cytokine measurement. Consent will be obtained by phone. Those providing consent will have blood (3mL-5mL EDTA tube and 5mL in sodium heparin tube) and marrow samples (3mL-5mL in EDTA tube and 5mL in sodium heparin tube) sent to the central laboratory for these studies. If samples have been donated and subject does not continue to transplant, samples will be stored for future research.
 - b. Health Related Quality of Life (Optional): At day +180 and day +365 post-HCT
The SRG will administer the 180 day and 1-year QOL instruments online, or on paper if requested by the patient. They will first confirm the patients' status with the transplant center because reporting of deaths may lag. They will then contact the patient via email, phone, or mail to collect the QOL information online or on paper.
At the conclusion of each QOL administration, patients will be reminded of the next date of contact. The SRG will notify the transplant center if a patient's contact information has changed, if they find through follow-up that the patient has died or that the patient wishes to be removed from future QOL surveys.

